#### 3. OBJECTIVES AND OUTCOME MEASURES/ENDPOINTS

The overall aim is to investigate the viability, credibility and acceptability (to patients, clinical pharmacists and GPs), and the fidelity of clinical pharmacists delivering the PROMPPT intervention to patients with persistent pain prescribed long-term opioids in primary care, and the feasibility of conducting a future cluster randomised controlled trial (cluster RCT) to determine clinical and cost-effectiveness.

# 3.1 Primary objectives

- Determine the availability and recruitment of eligible patients, the proportion scheduling and attending clinical pharmacist appointments and rates of retention at 3-month followup;
- 2. Determine the completeness of data collection;
- 3. Determine the fidelity of intervention delivery per protocol;
- 4. Determine the suitability of a self-reported pain medicines questionnaire and electronic medical records to calculate mean daily morphine equivalent dose;
- 5. Determine the suitability of the health resource use questionnaire for use in a future health economic evaluation;
- 6. Determine the potential barriers to and facilitators of successful delivery of the intervention:
- 7. Determine the acceptability and credibility of the intervention to patients;
- 8. Determine the acceptability of the intervention and training to Clinical Pharmacists and GPs, and the feasibility of delivering the intervention in general practice.

# 3.2 Secondary objectives

To use the study findings to:

- 1. Refine and optimise the PROMPPT intervention and associated clinical pharmacist training package;
- Refine sample size estimates for the main cluster randomised controlled trial (cluster RCT);
- 3. Refine and optimise the study design and processes, including self-reported patient questionnaires, for use in the main cluster RCT.

### 4 STUDY DESIGN AND SETTING

# 4.1 Study design

This study is a non-randomised feasibility study. We have chosen a non-randomised design for this feasibility study because the design of the proposed main trial in the final workstream of the PROMPPT research programme is a cluster RCT of a similar design to previous cluster RCTs conducted successfully by School of Primary, Community and Social Care, Keele University in a wide range of patients with musculoskeletal pain. Patient recruitment to these studies resulted in participation rates in the region of 40% of eligible patients with similar retention rates at both short term (greater than 75%) and 12 months follow-up (around 70%) in both intervention and control practices, and there was no evidence of selection bias. Therefore, we are confident in our ability to recruit and retain patients to a similar extent in both intervention and control arms of studies using this design and have included only an

intervention arm and not a control arm in this feasibility study. We will however monitor recruitment and retention rates in both intervention and control arms in an internal pilot within a main trial if this study demonstrates that progressing to a main trial is feasible.

The study design employs a theoretically informed mixed methods approach to meet the study objectives outlined in section 3. A nested mixed methods process evaluation will collect data regarding process outcomes from observations/audio-recordings of PROMPPT consultations, a patient self-reported acceptability questionnaire and semi-structured interviews with participating patients and clinicians. Data collection and analysis will be informed by the Theoretical Domains Framework (TDF) which identifies 14 related domains of influence on behaviour including knowledge, beliefs about capabilities, skills, motivation and goals. This will identify potential barriers and enablers for patients and clinical pharmacists to undertake behaviour change in relation to PROMPPT. The Theoretical Framework of Acceptability (TFA) will be used as an overarching framework to explore the acceptability of PROMPPT to clinical pharmacists, GPs and patients. Normalisation Process Theory (NPT) will be used to investigate the dynamics of implementing, embedding, and integrating PROMPPT, in order to identify potential process problems related to implementing PROMPPT.

# 4.2 Study Setting

PROMPPT-FS will be delivered from two general practices in the National Institute for Health Research (NIHR) Clinical Research Networks (CRN) West Midlands (CRN: WM) and two general practices in CRN: East Midlands (CRN: EM). Practices will invite patients to participate in the MOPP study. All MOPP study participants will be invited to a PROMPPT consultation.

### 4.3 Eligibility criteria

# 4.3.1 GP practices

Average sized (≥5,000 list size) GP practices will be eligible to participate if:

- The practice has a clinical pharmacist working in the practice for at least one session per week;
- The clinical pharmacist sees patients for face-to-face consultations in the practice;
- The clinical pharmacist is an independent prescriber;
- The clinical pharmacist consents to participate in the nested process evaluation including observation/audio-recording of a sample of PROMPPT consultations and an interview;
- One GP from the practice consents to an interview.

### 4.3.2 Individual patient participants

#### Inclusion criteria

- (1) Adult patients aged ≥18 years who are:
- (2) Prescribed any opioid analgesic (defined as any opioid or opioid/paracetamol combination analgesic from sections 4.7.2 and 4.7.1 British National Formulary (BNF) for chronic non-cancer pain continuously for ≥6 months, with a prescription issued within the previous 2 months.

#### Exclusion criteria

- (1) Patients with acute pain, cancer pain and/or terminal illness (life expectancy <6m);
- (2) Vulnerable patients (e.g. severe mental illness, learning difficulties, dementia);
- (3) Patients currently receiving treatment for substance misuse;
- (4) Patients who are unable to understand English.

### 4.4 Intervention

### 4.4.1 The PROMPPT intervention

PROMPPT is a clinical pharmacist-led intervention incorporating proactive review for patients who have been taking opioids regularly for at least 6 months and aims to reduce opioids, where appropriate, and to support self-management of persistent pain.

Best practice guidelines recommend review of patients taking opioids for persistent pain at least 6-monthly and gradual tapering of opioids where treatment goals are not met or when any modest benefit is outweighed by harm. In primary care, such reviews may be conducted by the GP or by another appropriately qualified healthcare professional, such as a clinical pharmacist.

PROMPPT was developed in line with guidance on development and evaluation of complex interventions using a person based approach combined with best practice guidance with theory (on behaviour change and normalisation of health care interventions) and stakeholder engagement during workstream one of this research programme. Extensive intervention development work included qualitative interviews with patients, clinical pharmacists and GPs, an online qualitative study (research discussion forum for people with experience of persistent pain and use of opioid medicines) and in-practice testing of prototype PROMPPT consultations in 3 GP practices with a clinical pharmacist. Findings have informed the study processes, intervention components and content of the training programme for clinical pharmacists. Specifically, findings identified that patients prioritise feeling respected and listened to and receiving individualised care, including relevant information resources and further support (e.g. referral or follow-up appointments), where appropriate. These findings also confirmed that the training programme needs to focus on developing clinical pharmacists' communication skills that support patient autonomy (e.g. respectful, values patient input, supports patient ownership of healthcare), understanding of pain conditions, knowledge of pain management and appropriate signposting and referral options.

Patients with persistent pain who have been prescribed opioids regularly for at least 6 months will be invited to schedule a PROMPPT pain review with the clinical pharmacist working at their GP practice. The clinical pharmacists will be independent prescribers and will complete specific training to deliver the PROMPPT intervention.

The invitation letter will be accompanied by a Pain Concerns Form. The Pain Concerns Form was developed from the Pain Concern Pain Navigator Tool with stakeholder engagement (including patients and a range of healthcare professionals) and in conjunction with a patient advisory (PPIE) group. The Pain Concerns Form is designed to help focus the consultation on the things that are most important to the patient. Patients are asked to complete the form, prior to their appointment, by reading a list of statements that represent concerns commonly

reported by patients with persistent pain, ticking those statements they agree with and adding any further concerns in a free text box.

The first consultation, (approximately 30 min) may be conducted face-to-face or remotely by video or telephone, depending on the impact of COVID-19 on service provision and any ongoing social distancing measures, and will begin with a holistic assessment of the patient's persistent pain including the impact of pain, followed by a personalised discussion to explore the patient's own experience of the effects (wanted/unwanted, useful/bothersome) of opioids, using information provided in the Pain Concerns Form where appropriate. Motivational interviewing techniques will be used to explore patient's reasons for considering changing their opioid medicines, their readiness to change and any ambivalence, before agreeing an individualised management plan.

Management plans will arise from shared decision making. The plan may include opioid tapering but this will not be mandatory, for example if the patient obtains continued useful benefit from moderate dose opioids, without experiencing troublesome side-effects. Where changes to medicines are agreed, SMART (specific, measurable, achievable, realistic, time-related) goal setting will be used to facilitate translation of intensions into action. Important barriers to reducing opioids specific to the individual, such as fear of pain worsening and/or withdrawal symptoms following opioid reduction will be addressed.

Management plans may also include advice and goals relating to self-management, signposting to information resources, signposting or referral to appropriate community services (for example physiotherapy, exercise classes and community psychology services) and, for more complex cases, discussion/collaboration with the GP and/or referral to specialist services if needed.

Follow-up will be arranged according to clinical need. Patients will also be provided with a clear plan for how to contact the clinical pharmacist between appointments if needed. Follow-up appointments may be conducted face-to-face or remotely by video or telephone, according to clinical need and patient preference, and are anticipated to be shorter in duration (no longer than 15 minutes).

### 4.4.2 The PROMPPT training package

The PROMPPT training package for clinical pharmacists will involve up to four training sessions. This training will cover communication skills, communication of risk and benefit in personalised discussions about opioids, motivational interviewing techniques, negotiating treatment plans, creating opioid tapering plans, optimising non-opioid pain management, supporting self-management for persistent pain, signposting to patient information resources and when to seek help (e.g. from GP). Training will also include self-care strategies to help clinical pharmacists manage any emotional impact of conducting pain reviews. A training manual will be supplemented by online training resources, for example videos of good and bad consultations, podcasts and written materials. In addition, clinical pharmacists delivering PROMPPT will be provided with regular mentoring by a multi-professional group of clinical champions.

Clinical pharmacists will also be provided with study-specific training including training on completion of study documentation, good clinical practice as applicable to research and the

maintenance of the study site file and study records. Reporting of serious adverse events and adverse events will also be covered.

Training will be provided by experts in pain management, primary care clinicians, behaviour change experts and medical/pharmacy educationalists.

Education/advice about the study will be provided for GPs in the participating practices to facilitate practice-wide engagement with the intervention and effective collaboration and ongoing support of clinical pharmacists.

### 5 STUDY PROCEDURES

### 5.1 Recruitment

# 5.1.1 Identification, recruitment and consent of GP practices (PROMPPT-FS)

The NIHR CRN: WM and CRN: EM will identify eligible general practices for the PROMPPT-FS as outlined in section 4.3.1. As part of the site identification process, a feasibility audit will be conducted by the CRNs to review the practice coding habits, to ensure that eligible patients can be identified and to ensure that the practice identified can meet the study requirements to deliver.

The study team will accompany CRN Research Facilitators to visit the identified practices to fully explain the study and describe the study requirements. Informed consent for practices to participate will be provided by the senior GP partner in each practice acting as 'guardian' for patients in their care, following agreement with their team clarifying willingness to undertake the PROMPPT intervention (see 5.1.3). GP practice consent to participate in the PROMPPT-FS will be formalised through written agreements. Eligible patients consenting to participate in the nested research evaluation (MOPP study) will receive the care which their practice is currently delivering for the PROMPPT-FS.

### 5.1.2 Identification and recruitment of participants (MOPP Study)

The PROMPPT-FS Health Informatic Specialist will design a search and report compatible with the participating practice GP System of Choice (GPSoC), to identify eligible participants as outlined in section 4.3.2. The search and report will be provided to the practice, to screen their electronic patient records to systematically identify adults prescribed opioid-containing pain medicines for 6 months or longer (with a prescription dispensed in the last two months), and grouped according to the strength of opioid medicine (weak, intermediate, strong). Grouping will be based on a published categorisation for prescribed analgesics in primary care. GPs will be asked to screen the patients identified according to the study inclusion and exclusion criteria, excluding ineligible patients.

Each patient identified will be assigned an individual study ID and their details will be mail-merged into a Consent to Contact invitation pack (to include an Invitation letter, a Participant Information Leaflet (PIL), a Consent to Contact form and reply paid envelope) inviting them to receive further information about the MOPP study. The Consent to Contact invitation pack will be sent via Docmail from the practice. Docmail is a standards-compliant hybrid mail service, providing document management and ISO 27001 secure mailings. Non-identifiable

sample demographic data (including age and sex, and opioid strength grouping) will be provided to the research team. This will allow any evidence of selection bias to be assessed.

Response rates to mail-outs will be monitored and, if needed, a further Consent to Contact invitation pack will be sent from the practice to non-responders after 2 weeks.

On receipt of a Consent to Contact invitation pack, the potential participant will complete the Consent to Contact form and return this in the pre-paid envelope provide to Keele Clinical Trials Unit (CTU), Keele University. Consent for Keele CTU to contact the potential participant providing them with further information regarding the MOPP Study will be obtained, in line with the definition outlined in Article 4(11) of the GDPR guidance, "any freely given, specific, informed and unambiguous indication of the data subject's wishes by which he or she, by a statement or by a clear affirmative action, signifies agreement to the processing of personal data relating to him or her" (European Union, 2016). Consent to be contacted with a MOPP Study invitation pack will therefore be implied by return of a completed Consent to Contact form.

On receipt of a completed Consent to Contact form, Keele CTU will mail potential participants a MOPP Study recruitment pack (to include; an invitation letter, Patient Information Leaflet, Baseline Questionnaire including consent form, and a prepaid envelope). A reminder postcard will be sent to non-responders after 2 weeks. A further reminder letter & recruitment pack will be mailed to non-responders after 4 weeks. A letter will be sent to participants where data is missing from consent forms in order to check that they are happy to take part in the study and that all required information is collected.

# Consent to participate

Consent to participate in the MOPP Study is provided by the potential participant in their completion and return of the MOPP Study Baseline Questionnaire and included consent form. Consent is requested for;

- Taking part in the MOPP Study (Read and understood the MOPP PIL, voluntary participation, completion of baseline and 3-month follow-up questionnaires).
- Depersonalised access to electronic medical records.
- Contact about future related research studies.

# 5.1.3 Identification and recruitment of participants (MOPP-2 Study)

Clinicians (GPs and clinical pharmacists) working at the identified practices, will be invited to participate in the nested process evaluation (MOPP-2 study). Participant Information Leaflet and reply forms will be provided. The Clinical pharmacist from each participating practice will be asked to consent to observation/audio-recording of a sample of PROMPPT consultations (with patient consent) and to an interview. GPs at each practice will be asked to consent to an interview. When Keele CTU has received signed interview reply forms from one clinical pharmacist and from one GP working in an identified GP practice, eligibility of that practice is confirmed and the CRN will complete recruitment of the practice.

### Observation /audio-recording of consultations

The research team will work with participating practices to identify and approach patients who are suitable to take part in the pain review observation/audio recording study.

A member of the research team will attend participating GP practices for a sample of consultations and will invite patients to consent to observation and/or audio-recording of the consultation, with the aim of observing and/or audio-recording two consultations per practice.

Informed, written consent to observe or audio-record the consultation will be obtained from patients attending for face-face consultations and confirmed with clinical pharmacists prior to the start of the consultation. For remote consultations by video or telephone, an information leaflet will be sent in advance of the consultation, and the researcher will read through and complete the consent form with the participant over the telephone; this will be undertaken verbally and recorded prior to the remote consultation commencing. The research team will inform clinical pharmacists which participants have agreed. The participant will then send back a signed consent form on completion of the consultation.

If patients consent to this, consultations will be audio-recorded using a digital audio-recorder, which will be switched on by a researcher or the clinical pharmacist prior to the start of the consultation. Following the consultation, the researcher or clinical pharmacist will securely send the audio recording to Keele CTU for analysis.

# Acceptability Questionnaire

Following the initial consultation with the practice clinical pharmacist, participants who gave consent to future contact about related studies, will be mailed a MOPP-2 recruitment pack by Keele CTU. The MOPP-2 Recruitment pack will include an invitation letter, Participant Information Leaflet, Acceptability Questionnaire (including consent form), an Interview Reply Slip and a prepaid envelope. Participants may choose to consent to any, all or none of these options.

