#### Patient Interviews

Patient participants who return the Interview Reply Slip consenting to further contact for an interview, will be contacted by a researcher to arrange a mutually convenient time and location for this. Interviews may be conducted face-to-face or by telephone. Face-to-face interviews are likely to take place in the participants' own home. When interviews take place in a person's home, they will be conducted in accordance to Keele University's lone working guidelines. The qualitative researcher(s) and a nominated contact will follow standard procedures regarding contact before and after the interview.

An interview confirmation letter will be sent specifying the date, time and location (or telephone number). A letter will be sent to the participant's GPs informing them that their patient is taking part in an interview. Once the target sample size of 15 participants has been reached, all subsequent participants who return their interview reply form will be sent a letter thanking them for their interest and informing them that we will not be inviting them to take part on this occasion.

Fully informed consent will be obtained prior to all interviews commencing.

For telephone interviews, the researcher will read through and complete the consent form with the participant over the phone; this will be undertaken verbally and recorded prior to the interview commencing. The participant will then send back a signed consent form on completion of the interview.

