### Acceptability Questionnaire

All participants who attended the clinical pharmacist appointment will be mailed a short survey (known as the Acceptability Questionnaire) about their experiences of the consultation, which will supplement the qualitative data. This short survey will have a total of 12 questions from two existing measures: a modified version of the treatment acceptability and credibility measure and the Theoretical Framework of Acceptability (TFA) questionnaire. The modified acceptability and credibility measure has been used in previous similar studies. The measure includes 4 items, (scored on a 0-10 scale) and will assess (1) how logical the PROMPPT Intervention seems to participants, (2) how confident participants are that it will be successful in helping them (3) how confident participants would be in recommending it to a friend and (4) how satisfied they were with the intervention overall.

The TFA questionnaire comprises 8 items (scored on a 0-5 scale) . The first is a global acceptability question and the remaining 7 (items 2-8) represent key constructs of

acceptability relating to healthcare interventions (affective attitude, burden, intervention coherence, ethicality, perceived expectations, opportunity cost, and self-efficacy).

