#### Semi-structured interviews

Patient participants will be interviewed after attending at least one appointment with the clinical pharmacist. The interviews will be based on semi-structured topic guides developed in association with our PPIE group and will include questions informed by our programme theories regarding behaviour change, implementation and acceptability. Topic guides will be refined during data collection to allow any emerging issues to be explored. A similar process will be followed for the clinician participants whereby they will be interviewed once they have experience of PROMPPT intervention delivery.

We expect that up to 15 patients (sampled from across the 4 participating practices) and approximately 8 clinicians, n=4 GPs and n=4 clinical pharmacists (one of each from each participating practice) will be sufficient to attain rich data. We will cover similar topics with all interviewees to ensure we can compare their responses, while at the same time enabling them to reflect on their specific expectations, understandings and experiences. All interviews will be conducted by an experienced qualitative researcher. With the participants' consent, interviews will be audio recorded. The interviews will be securely sent to a professional transcription company (The Transcription Company UK) who operate under the terms of a confidentiality agreement and who have an existing contract with Keele CTU. Transcripts will be transcribed verbatim. Transcripts will be anonymised by members of the research team ahead of analysis.

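### The protocol gives two conflicting mailing rules for the Acceptability Questionnaire, so the population behind the acceptability progression criterion is contradictory, and no step secures the promised spread of interviews over practices

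*Protocol*

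**What the plan says.** **Questionnaire.** Section 5.1.3 (Acceptability Questionnaire) states that, after the initial consultation, "participants who gave consent to future contact about related studies, will be mailed a MOPP-2 recruitment pack". The questionnaire and an interview reply slip are both in that pack, and "Participants may choose to consent to any, all or none of these options". The consent that acts as the filter is an item of its own in the baseline consent form (section 5.1.2, Consent to participate): "Contact about future related research studies". Section 5.3.2 (Acceptability Questionnaire) gives a different rule: "All participants who attended the clinical pharmacist appointment will be mailed a short survey".

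**Use of the score.** Section 6.5 makes a mean of at least 5 on items 9-12 one of five progression criteria. Section 6.2.8 applies the threshold to each of the four items. Neither sets a minimum response.

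**Interviews.** Section 5.1.3 (Patient Interviews) has a researcher contact those who return the slip. It then says: "Once the target sample size of 15 participants has been reached, all subsequent participants who return their interview reply form will be sent a letter" declining the offer with thanks. Section 5.3.2 (Semi-structured interviews) plans for "up to 15 patients (sampled from across the 4 participating practices", and adds: "Patient participants will be interviewed after attending at least one appointment with the clinical pharmacist".

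**The concern.** Sections 5.1.3 and 5.3.2 cannot both be followed. An attender who did not agree to future contact is mailed the questionnaire under one and not under the other. The choice fixes who can contribute to a progression criterion.

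Under 5.1.3 the score passes through two voluntary filters after attendance: agreeing at baseline to be approached about further research, and returning the form. Each plausibly favours people well disposed to the study. Section 5.1.3 describes no reminder for this pack, whereas sections 5.1.2 and 5.3.1 describe reminders for the baseline and 3-month questionnaires. The first filter is avoidable, because 5.3.2 already describes mailing without it.

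The interviews feed another progression criterion. Section 5.3.2 promises a sample drawn from all four practices, but the only procedure given (contact those who reply, decline repliers after the fifteenth participant) contains nothing that would produce that spread.

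**Working it through.** **Inputs from the protocol.** 80 participants (Study Summary; section 6.1). Threshold of 5 on items scored 0-10 (sections 5.3.2, 6.2.8, 6.5). Attendance criterion above 50%, so at least 41 of 80 (section 6.5). 15 patient interviews, 4 practices. The protocol gives no expected number or precision for the acceptability score, so there is no stated figure to reproduce.

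**Assumed inputs (not in the protocol).** Attendance 60%. Agreement to future contact 80%, range 60-100%. Return 65%, range 40-80%. Responder mean 6.5, also tried at 6 and 7.

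**Formula.** Let *A* be attenders, *R* responders, *m* the responder mean and *x* the mean that non-responding attenders would have given. The mean over all attenders is [*mR* + *x*(*A* − *R*)] / *A*. Setting this to 5 gives

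*x* = (5*A* − *mR*) / (*A* − *R*).

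If the non-responder mean is below *x*, a pass among responders would be a fail among attenders. With *r* = *R*/*A* this is *x* = (5 − *mr*)/(1 − *r*), so the attendance rate cancels and only the response share and *m* matter.

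**Section 5.1.3 rule, central assumptions.**
- *A* = 80 × 0.60 = 48
- *R* = 48 × 0.80 × 0.65 = 24.96, about 25 (52% of attenders)
- *x* = (5 × 48 − 6.5 × 25) / (48 − 25) = 77.5 / 23 = 3.4

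**Section 5.3.2 rule, same assumptions**, further assuming that those who withheld future-contact consent return the form at the same 65%.
- *R* = 48 × 0.65 = 31.2
- *x* = (240 − 6.5 × 31.2) / (48 − 31.2) = 37.2 / 16.8 = 2.2

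Dropping the filter raises the response share from 52% to 65%. Non-responders would then have to be considerably more negative to overturn a pass.

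**Range at *m* = 6.5.**
- Lowest response, *r* = 0.60 × 0.40 = 0.24: *x* = (5 − 1.56)/0.76 = 4.5
- Highest response, *r* = 1.00 × 0.80 = 0.80: *x* = (5 − 5.2)/0.20 = −1.0, off the scale, so the result cannot be overturned

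**Other responder means.** At *r* = 0.24, *x* is (5 − 1.44)/0.76 = 4.7 for *m* = 6 and (5 − 1.68)/0.76 = 4.4 for *m* = 7. At *r* = 0.80, *x* is (5 − 4.8)/0.20 = 1.0 for *m* = 6 and impossible for *m* = 7.

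**Number of people behind the score.** At the smallest attendance that passes, it is 41 × 0.24 = 9.8 to 41 × 0.80 = 32.8, so about 10 to 33.

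**Interviews.** Without a per-practice limit, the text guarantees no minimum from any practice. With a limit of 4, three practices can supply at most 3 × 4 = 12 of the 15, so the fourth must supply at least 15 − 12 = 3.

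**The case against.** **Low stakes.** Section 6.2 calls the quantitative analysis exploratory. Section 6.2.8 weighs the scores alongside qualitative data, and a missed criterion leads to discussion with the steering committee, not to a stop. This stands, and it limits the weight of the point. It does not settle which mailing rule applies.

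**Upward bias as a fact.** A reader might infer that acceptability is shown to be biased upward. The protocol does not support that. A conflict between two mailing rules has no direction, dissatisfied patients may also reply, and no rate is given from which a size could be derived.

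**Non-attenders.** A reader might go further and say that the study hears nothing from people who stay away, or extend the calculation to all 80 participants. Neither holds. Non-attenders are sent the 3-month questionnaire (section 5.3.1), and the practice telephones those who have not booked (section 5.2). Attendance has its own progression criterion, and section 6.4 reads uptake together with the acceptability scores. The survey asks about experience of the consultation, so people who never had one have no score to impute. The calculation is therefore confined to attenders.

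**First come, first served.** A reader might infer this from the cut-off at 15, or conclude that early practices could take every place. The protocol states neither the rule nor a sequential start of practices. A cap and a spread over practices can both be honoured, so these passages do not contradict each other. What stands is that no step delivers the spread. Pharmacist and GP interviews also address acceptability (section 4.1), so the interview criterion need not rest on patients alone.

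**The opposite reconciliation.** Section 5.3.2 could be narrowed to match 5.1.3, which respects the consent as now worded. That would end the contradiction but keep the filter. The consent argument does stand to this extent: the wider mailing needs matching consent wording.

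**Conclusion.** The concern holds in a limited form. Sections 5.1.3 and 5.3.2 disagree on who is mailed the Acceptability Questionnaire, so the population for one of the five progression criteria is contradictory. Under 5.1.3 the score is open to a selection step that the protocol could avoid. Its effect is probably upward, but that is a judgement and not a result.

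Whether selection could change the decision depends on response. Under the assumed central rates and a responder mean of 6.5, attenders who did not respond would have to average below about 3.4. At 24% response the figure is about 4.5, which is easily reached. At 80% response a mean of 6.5 is safe. These figures rest on assumed attendance, contact-consent and return rates and an assumed mean, and apply to each item separately if section 6.2.8 governs.

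The interview point is one of missing procedure: the promised spread over four practices is not secured. The changes are small and should be made before mailing, because views not collected at the time are hard to recover afterwards.

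**What to change.** 1. **One mailing population.** Adopt the section 5.3.2 rule and mail the questionnaire to every attender. In section 5.1.3, remove the future-contact condition for the questionnaire (the interview slip may keep it). Align the MOPP consent form and leaflet so that this mailing is covered by consent to the main study.
2. **Report the criterion with its denominator.** In sections 6.2.8 and 6.5, give the numbers who attended, were mailed and returned the form. Compare responders with non-responders among attenders on baseline data. State the non-responder mean that would bring the attender mean below 5.
3. **Secure the interview spread.** In section 5.1.3 (Patient Interviews), cap interviews at about 4 per practice and hold later replies in reserve instead of declining them. State when reserve replies may be released if a practice cannot fill its places.

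Cost: a minor amendment to consent, leaflet and mailing wording, a few more questionnaires to post, and interviews that may finish slightly later. The total stays at 15.
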